4.3 Subject Recruitment and Screening

Potential subjects will be recruited from the clinical practice of the principal investigator (PI) at the time of their routine eye examination visit. The clinical practice is located in the Illinois Eye and Ear Infirmary, Department of Ophthalmology and Visual Sciences, University of Illinois at Chicago. Subjects will

include patients who have been diagnosed with dry eye in the investigator's eye clinic (cornea clinic or the comprehensive eye clinic), in the Illinois Eye and Ear Infirmary. Patients may also be referred to the PI's clinic by other Ophthalmology physicians at UIC, and Ophthalmology physicians at Loyola and North-Western Universities. The referring physicians shall inform the patients briefly about the study and provide them with the recruitment flier/ information sheet (enclosed), but no study related procedures (including screening and recruitment) will be performed at any location outside the PI's clinic at UIC (Illinois Eye and Ear Infirmary). Even the patients referred to the PI's clinic for possible enrollment in the study, will be screened and, if eligible, recruited in the study only at the PI's clinic. The physician letter (requesting for referrals for the study by the PI), and the information sheet that will be given to the subjects are attached.

Patients with established Dry Eye Disease (for at least 6 months, with Schirmer I < 10 and annoying or activity limiting visual symptoms) will be approached by a member of the research staff to determine if the patient might be interested in participating in a research study. If the patient is interested, the research staff member will describe the study. If the patient is willing to enter the study, the study will be discussed and the patient will be asked to sign the informed consent form. Consent will be obtained prior to screening to determine eligibility. Screening procedures include documentation of prior Dry Eye Disease as well as other assessments as detailed in section 6.5.1. Eligible patients will be enrolled in the study.

4.4 Early Withdrawal of Subjects

4.4.1 When and How to Withdraw Subjects

Subjects have the right to withdraw from the study at any time, for any reason, without jeopardizing their medical care. Where possible, subjects will be followed for safety and encouraged to return for follow-up visits for any unresolved safety events.

The IRB and Investigator also have the right to withdraw subjects from the study for the following reasons: when continuation may jeopardize the health of the subject, protocol violations, adverse events or concurrent conditions, administrative or other reasons.

4.4.2 Data Collection and Follow-up for Withdrawn Subjects

If a subject withdraws from the study prior to 8 weeks, the subject will be asked to complete the procedures outlined in the 10 week visit as well as the Test Substance Tolerance scale from 8 weeks, as soon as possible. Subjects who voluntarily withdraw from the study between 8 weeks and 10 weeks will be asked to complete procedures outlined in the 10 weeks visit as soon as possible. Subjects who are withdrawn due to adverse events will be followed at least until resolution or stabilization of the adverse event.

If the subject remains in the study for safety evaluation, follow-up visits will be scheduled according to the schedule of visits and procedures found in the synopsis.

5 Study Drug

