6.5.3	Visit 3: Week 2 (\pm 2 days)	25
6.5.4	Visit 4: Week 4 (\pm 2 days)	25
6.5.5	Visit 5: Week 6 (\pm 2 days)	26
6.5.6	Visit 6: Week 8 (\pm 2 days)	26
6.5.7	Visit 7: Week 10 (\pm 2 days)	26
7	STATISTICAL PLAN	26
7.1	SAMPLE SIZE DETERMINATION	26
7.2	STATISTICAL METHODS	27
7.3	SUBJECT POPULATION(S) FOR ANALYSIS	27
8	SAFETY AND ADVERSE EVENTS	27
8.1	ADVERSE EVENT DEFINITIONS	27
8.2	CLASSIFICATION OF ADVERSE EVENTS BY SEVERITY	28
8.3	CLASSIFICATION OF ADVERSE EVENTS BY RELATIONSHIP TO STUDY TREATMENT	28
8.4	ACTION(S) TAKEN	29
8.5	OUTCOME	29
8.6	ADVERSE EVENT REPORTING	29
8.7	SERIOUS ADVERSE EVENT REPORTING	29
8.8	IN CASE OF AN EMERGENCY	30
8.9	DATA SAFETY MANAGEMENT PLAN	30
8.10	STUDY OVERSIGHT	30
9	CONFIDENTIALITY	31
10	SOURCE DOCUMENTS	31
10.1	RECORDS RETENTION	31
11	ETHICAL CONSIDERATIONS	31
12	STUDY FINANCES	32
12.1	FUNDING SOURCE	32
12.2	CONFLICT OF INTEREST	32
12.3	SUBJECT STIPENDS OR PAYMENTS	32
13	REFERENCES	33

SCHEDULE OF VISITS AND PROCEDURES

	Screening	Day 1 (Pre-Dose)	Day 1 (Post-Dose)	Week 2	Week 4	Week 6	Week 8	Week 10
Informed Consent	X							
Demographic Information	X							
Medical History/Con Meds	X							
Ophthalmic/Dry Eye History	X							
Vital Signs		X		X	X	X	X	X
Ophthalmic Examination (Slit lamp)	X	X		X	X	X	X	X
Ocular surface redness score	X	X		X	X	X	X	X
Schirmer 1 test and Rose Bengal staining	X						X	
Pregnancy Test (urine)*	X							
Best Spectacle Corrected Visual Acuity		X						X
Randomization visit		X						
First Study Medication		X						
Drug dispensation visits			X	X	X	X		
Instruction on study medication self-administration			X					
Ocular Surface Disease Index (OSDI)		X		X	X	X	X	X
Visual Analogue Scale (VAS)			X	X	X	X	X	
Physical inspection of nose & oropharynx				X	X	X	X	X
Clinical Global Impression (CGI)		X		X	X	X	X	X
Subject Global Assessment (SGI)		X		X	X	X	X	X
Adverse Events/ Concomitant Medications		X	X ⁺⁺	X	X	X	X	X

*If applicable ++ AEs only

ABBREVIATIONS

AE	Adverse Event
APC	Antigen-presenting cells
BSCVA	Best Spectacle Corrected Visual Acuity
EC	Ethics Committee
eDNA	Extracellular DNA
CNL	Corneal Neurobiology Laboratory
CRF	Case Report Form
CGI	Clinical Global Impression
DCF	Data Clarification Form
DED	Dry Eye Disease
DNase I	Deoxyribonuclease I
FDA	Food and Drug Administration
FVC	Forced vital capacity
GCP	Good Clinical Practice
ICH	International Conference on Harmonization
IB	Investigator's Brochure
IOP	Intraocular pressure
IRB	Institutional Review Board
KCS	Keratoconjunctivitis sicca

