6.5.6 Visit 6: Week 8 (\pm 2 days)

Treatment Visit (after any dose for that day)

- Vital Signs
- Ophthalmic Examination (slit lamp examination, Ocular surface redness score, Rose Bengal staining, and a Schirmer 1 test)
- Physical Inspection of the Nose and Oropharynx
- OSDI
- Test Substance Tolerance
- Clinical Global Impression, Subject Global Assessment
- Review the subject's diary and record changes in concomitant medication, deviations from drug schedule and adverse events.

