6.5.7 Visit 7: Week 10 (\pm 2 days)

Follow-Up Visit

- Vital Signs
- Ophthalmic Examination (slit lamp examination, Ocular surface redness score)
- Physical Inspection of the Nose and Oropharynx
- BSCVA (Snellen)
- OSDI
- Clinical Global Impression, Subject Global Assessment
- Review the subject's diary and record changes in concomitant medication and adverse events.

7 Statistical Plan

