7.3 Subject Population(s) for Analysis

Subject population for analysis will include any subject enrolled in the study who received at least two weeks of treatment with study eye drops and attended at least the first post-treatment (week 2) follow up visit.

8 Safety and Adverse Events

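### Subjects who leave before Week 8 and are not kept on schedule for safety follow-up have no post-baseline staining or Schirmer value, because the withdrawal visit omits both tests

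*Combined protocol and SAP*

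**What the plan says.** Section 4.4.2 governs early withdrawal. For a subject leaving before 8 weeks, "the subject will be asked to complete the procedures outlined in the 10 week visit", and the only Week 8 item carried over is the tolerance scale. The section makes one exception: "If the subject remains in the study for safety evaluation, follow-up visits will be scheduled according to the schedule of visits and procedures" in the synopsis.

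The Week 10 list (6.5.7) has "Ophthalmic Examination (slit lamp examination, Ocular surface redness score" and stops there. It also includes BSCVA, OSDI, CGI and SGA. The Week 8 list (6.5.6) has "Ocular surface redness score, Rose Bengal staining, and a Schirmer 1 test". In the Schedule of Visits and Procedures, the row "Schirmer 1 test and Rose Bengal staining" carries two marks, Screening and Week 8. The lists for Weeks 2, 4 and 6 (6.5.3 to 6.5.5) give slit lamp and redness only.

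Section 3.2 makes reduction in Rose Bengal staining primary efficacy endpoint (2), assessed after 8 weeks of treatment. The synopsis names only OSDI change as the primary efficacy measure. Section 3.3 lists Schirmer change and complete staining clearance as the first two secondary endpoints.

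Section 7.3 analyses anyone who had at least two weeks of treatment and "attended at least the first post-treatment (week 2) follow up visit". Section 7.2 gives no method for missing data.

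**The concern.** The analysis population is deliberately wider than the completers, but for staining, clearance and Schirmer the data collection supports only those who reach a Week 8 examination. A subject who leaves at Week 4 or Week 6 counts in the 7.3 population and contributes nothing to these three endpoints. Section 4.4.2 recognises that the Week 10 list lacks something needed from Week 8, since it carries over the tolerance scale, but it does not do the same for the other two tests.

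The missing subjects are unlikely to be a random subset. Under sections 5.6 and 5.7, a subject who worsens and restarts anti-inflammatory therapy, or stops study drug, is taken out of the study. Some of the subjects doing worst may therefore go before the single post-baseline staining measurement. If such exits differ between arms, the staining comparison is distorted, and no earlier staining score exists to show by how much.

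**Working it through.** **Where each measure is taken, by the visit lists**

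| Measure | Status | Weeks 2, 4, 6 | Week 8 | Week 10 | Withdrawal visit before Week 8 |
|---|---|---|---|---|---|
| OSDI | primary (synopsis and 3.2) | yes | yes | yes | yes |
| CGI, SGA | anchors to OSDI (3.2) | yes | yes | yes | yes |
| Redness | primary (3.2) | yes | yes | yes | yes |
| Rose Bengal staining | primary (3.2 only) | no | yes | no | **no** |
| Staining clearance | secondary (3.3) | no | yes | no | **no** |
| Schirmer | secondary (3.3) | no | yes | no | **no** |
| Tolerance scale | primary tolerability (3.2) | yes | yes | no | yes, carried over |

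The gap is confined to the three measures that need Rose Bengal or Schirmer.

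**The plan's own figure.** Section 7.1 enrols 72 so that a 20% loss still leaves at least 30 completers per group.
- 72 x (1 - 0.20) = 57.6 completers, or 28.8 per arm if the arms are equal, so the stated aim is not reproduced.
- 60 / 0.80 = 75 would be needed. The 72 matches 60 x 1.20. With 72 enrolled, 60 complete only if the loss is at most 1 - 60/72 = 16.7%.
- This is a separate matter. The present point uses only the 72 and the 20%.

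**Upper bound on subjects affected.** Number without a value = 72 x non-completion rate x share who leave before Week 8 without being kept for safety evaluation.
- 20% rate, share 100%: 72 x 0.20 = 14.4
- 20% rate, share 75% (assumed): 14.4 x 0.75 = 10.8
- 20% rate, share 50% (assumed): 14.4 x 0.50 = 7.2
- Other rates (assumed), share 100%: 5% gives 3.6, 10% gives 7.2, 30% gives 21.6

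These counts include subjects who leave before Week 2. They fall outside the 7.3 population, so the loss within the analysed set is smaller.

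**What adding the tests would recover.** Taking the upper bound, number with a post-baseline staining value = 57.6 + 14.4 x attendance at the withdrawal visit (attendance assumed).
- 0%: 57.6
- 50%: 57.6 + 7.2 = 64.8
- 80%: 57.6 + 11.5 = 69.1
- 100%: 72

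**The case against.** Several counter-arguments have force.

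- **Safety exception.** A reader might infer that everyone who leaves before Week 8 lacks these values. The documents do not support that: subjects kept for safety evaluation follow the normal schedule and could have the Week 8 tests, and 4.4.1 encourages return for unresolved safety events. This stands and limits the point to those who actually leave.
- **Status of staining.** A reader might infer that primary efficacy as a whole is compromised. It is not: OSDI, the only primary efficacy measure in the synopsis, is in the Week 10 list, as are CGI, SGA and redness. Staining is primary only under 3.2, and the two statements should be reconciled. Whichever prevails, all three affected endpoints keep the gap.
- **Size.** A reader might take about 14 as the expected loss. It is a ceiling: the 20% is an allowance for not completing a study that runs to Week 10, and 4.4.2 separately provides for leavers between Weeks 8 and 10, who would already be due the Week 8 tests. Section 8.1 allows replacement of adverse-event withdrawals, but that adds subjects without supplying the missing values.
- **Auxiliary data.** OSDI and redness are recorded every two weeks, and the slit-lamp examination records superficial punctate keratopathy (3.4.2). These could inform a model for missing staining. They are not Rose Bengal scores, however, and 7.2 plans no such model.
- **A withdrawal value is not a Week 8 value.** The endpoint is defined after 8 weeks of treatment. A Week 3 score, or one taken after anti-inflammatory therapy was restarted, measures something else, and substituting it directly could introduce a different bias. This stands and shapes the fix.

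**Conclusion.** The gap is real and follows from applying the protocol as written. Subjects who withdraw before Week 8 and are not kept on schedule for safety evaluation have no post-baseline staining, clearance or Schirmer value, although those who reached Week 2 are in the analysis population. The analyses of these three endpoints then rest in effect on subjects examined at Week 8.

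At the protocol's 20% allowance, up to about 14 of 72 subjects are affected, and about 7 if half of the non-completers leave before Week 8 (an assumed share). The ceiling assumes that every non-completer leaves before Week 8 and that none is kept on schedule.

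The loss is likely to be informative, given sections 5.6 and 5.7. A reader might go further and infer that the bias favours one arm. Section 1.5 mentions a risk of worsening on placebo, but nothing in the documents gives withdrawal rates by arm, so the direction cannot be stated. The change should be made: it is small, and values not taken at withdrawal cannot be recovered later.

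**What to change.** - **Section 4.4.2:** add Rose Bengal and Schirmer to the visit for withdrawals before Week 8. Keep the Week 10 list, including BSCVA, and the tolerance scale. Make the Schedule of Visits and Procedures agree.
- **Section 7.2:** keep the Week 8 value as the main staining and Schirmer analysis. Prespecify a sensitivity analysis that uses the withdrawal-visit values, with their timing recorded and those taken after anti-inflammatory therapy was restarted flagged. Do not treat them as Week 8 values.
- **Synopsis and section 3.2:** reconcile whether staining is a primary endpoint.

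The cost is short edits to the text and slightly longer testing at a visit the plan already asks for, using tests the site already performs. The limit is attendance: subjects are asked to come, not required to, so recovery may fall anywhere from none to all of the missing values.

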5.1 Description

The study drug, rhDNase1, will be supplied as a 1 mg/ml (0.1%) solution for administration as topical eye drops. The control group will receive drug vehicle eye drops as placebo.

Each subject will receive either 0.1% rhDNase1 (study drug) or drug vehicle (placebo) solution, as a single eye drop in each eye four times a day (QID) for eight weeks. Except for the first dose on Day1, subjects will self-administer the test medication eye drops at home.

Subjects will not be charged for the test medication in any way (neither the cost of the medication nor its dispensing cost).

5.2 Treatment Regimen

Study drug group- rhDNase1, 1mg/ml (0.1%) eye drops will be applied to both eyes q.i.d for 8 weeks. Control group - drug vehicle eye drops will be applied to both eyes q.i.d for 8 weeks. For either group, the patient will be instructed to instill the first dose of the study medication in the morning at approximately 8 a.m., and then the remaining doses at approximately 4 hourly intervals. Therefore, doses will be scheduled at approximately 8 a.m., 12 noon, 4 p.m. and 8 p.m.

5.3 Method for Assigning Subjects to Treatment Groups

This Randomized placebo-controlled trial will have two study groups. Subjects will be randomly assigned to one of two groups (#1, #2). Group #1 will receive placebo (drug vehicle; control group) and Group #2 will receive study drug (rhDNase 0.1%; test group). We will use a computer-based random code generator (Research Randomizer; <http://randomizer.org/>) to generate 1 set of 72 non-unique, unsorted numbers with a range from 1 to 2 representing the group number (#1 is control group, #2 is test group). Each subject will be assigned a study identification (ID) number at screening, eg. subject #1, subject #2, subject #3 and so on. Based on the randomizer generated table, subject #1 will receive either placebo (#1 group) or study drug (#2 group). This will be repeated for each subject. For reproducibility purpose, we will document the final randomization schedule and the random SEED number used to generate the schedule. Randomization will be performed by the Illinois Eye and Ear Infirmary's pharmacy, and neither participants nor research staff will be aware of the assigned treatments. The person conducting the randomization will remain masked as well.

The study identification (ID) number will be used on all study-related documents. To maintain confidentiality, the subject's name will not be recorded on any study document other than the informed consent form. The drug vial number will be linked to the patient identification number.

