3.1 General Design

This will be a Randomized controlled trial, in which a total of 72 patients will be enrolled at 1 clinical site. Subjects will be randomly assigned to one of two groups (#1, #2), with at least 30 subjects per group. Group #1 will be given placebo (drug vehicle- eye drops without rhDNase 0.1%) and Group #2 will be given study drug (rhDNase 0.1%).

Patients with established Dry Eye Disease will be approached by a member of the research staff to determine if the patient might be interested in participating in a research study. If the patient is interested, the research staff member will describe the study. If the patient is willing to enter the study, the study will be discussed and the patient will be asked to sign the informed consent form. Consent will be obtained prior to screening to determine eligibility. Screening procedures include documentation of prior Dry Eye Disease. Eligible patients will be enrolled in the study.

All enrolled subjects will receive their first dose of test medication (placebo/ study drug) on study Day 1 in the doctor's office and after completion of the study assessments, will have the topical eye drops dispensed for self-administration. See Section 5.4 *Preparation and Administration of Study Drug* for details.

Subjects will be provided with diaries to record the time of each dose and will also be asked to record any adverse symptoms. In addition, they will be asked to make a note of any missed doses together with the reason for the omission. Subjects will return two weeks later on Day 14 for further study assessments, thereafter at 4 weeks, 6 weeks and 8 weeks (the last day of treatment), and again at 10 weeks after two weeks of no treatment with study drug for the final study assessments.

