The subjects will be monitored frequently (at 2 weekly intervals) to ensure that they are not subjected to any undue risks during the wash out period or during the course of the study. Additionally, they will be warned of the possible signs and symptoms of clinical worsening of DED, and advised to contact the research team immediately in case any of those symptoms occur. Subjects will also be encouraged to contact the research team in case they experience any ocular discomfort during the wash out period or during the course of the study. The subject's condition will be monitored by the physician (Principal Investigator) at each study visit, as well as at any interim visit (in case of adverse symptoms, as mentioned above). Any worsening of DED or any adverse event due to the study drug will be recorded. In case of clinical worsening, based on the individual subject's clinical condition, one or more of the following therapeutic decisions may be implemented: (1) Increasing the frequency of use of artificial tears, (2) Re-starting the use of anti-inflammatory therapy (Restasis/ corticosteroids), (3) Withdrawal of the use of study drug (if worsening occurs during the course of the study). The decision will be made by the physician (Principal Investigator) based his clinical judgment as per the individual subject's clinical condition. If additional anti-inflammatory therapy (Restasis/ corticosteroids) is instituted during the wash-out period, the subject will be excluded from the study. Also, if additional anti-inflammatory therapy (Restasis/ corticosteroids) is instituted during the course of the study and/or the study drug is

withdrawn, the subject will be excluded from the study. After any clinical worsening is noted, the subjects will be followed more closely (weekly) until complete resolution of symptoms and return to the subject's previous baseline.

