6.2 Assignment of Patient Identification

A study identification (ID) number will be assigned to each subject at screening. This study ID number will be used on all study-related documents. To maintain confidentiality, the subject's name will not be recorded on any study document other than the informed consent form. The master code list will link the subject MRN to the study ID number given to each subject. The master code list will be stored on the desktop in PI's OFFICE in Lions of Illinois Eye Research Institute (LIERI). The data collected and master code list will be accessible only to the PI and the research team involved in this project. The desktops will be password protected as well. Data will not be shared over the internet and will remain password protected. Confidentiality will be maintained. Data will be de-identified once study is completed and for subjects determined to not meet eligibility criteria or who later decline participation in the consent process.

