8.1 Adverse Event Definitions

The following are specific definitions of terms guided by the International Conference on Harmonization (ICH) Guidelines for Good Clinical Practice (GCP) and the U.S. Code of Federal Regulations that apply to this section:

Adverse Event: Any untoward medical occurrence in a subject or clinical investigation subject administered a pharmaceutical product and which does not necessarily have to have a causal relationship with this treatment. An adverse event can be any unfavorable sign (including an abnormal laboratory finding), symptom, or disease temporally associated with the use of the investigational product, whether or not considered related to the investigational product.

Subjects will be reminded to inform the study staff of any adverse effects that they have experienced or are experiencing after the first administration of study drug. In addition, subjects will record adverse events in their diary throughout the study. All reports of adverse events during the study will be recorded on an Adverse Event Case Report Form (CRF). The subject should not be prompted about any adverse events that may occur during this trial.

For each adverse event, the following information will be recorded on the subject's Case Report Form(s): onset date, end date or continues, intensity, duration, relationship to test patch, action taken, and outcome. If a subject experiences a serious adverse event (SAE), study staff may discontinue the subject from study participation. The study staff must notify the IRB within 24 hours of receipt of the information. The study staff will instruct the subject to notify the research facility should any adverse

event occur within 7 days of study completion. (For definitions of an AE and SAE, see below). Subjects who withdraw due to an adverse event may be replaced.

- **Serious Adverse Event:** An untoward medical occurrence that at any dose:
 1. results in death
 2. is life-threatening
 3. requires inpatient hospitalization or prolongs existing hospitalization
 4. results in persistent or significant disability/incapacity
 5. is a congenital anomaly/ birth defect
 6. requires medical or surgical intervention to prevent any of the occurrences noted above.

- **Life-threatening:** Any adverse drug experience in which the subject was at risk of death at the time of the event. It does not refer to an event which hypothetically might have caused death if it were more severe.

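### Sections 5.3 and 6.2 tie a fixed, unblocked list of 72 allocations to ID numbers issued at screening, while the Schedule and Section 6.5.2 place randomisation on Day 1; the passages must be reconciled.

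*Combined protocol and SAP*

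**What the plan says.** Section 5.3 uses a web randomiser "to generate 1 set of 72 non-unique, unsorted numbers with a range from 1 to 2 representing the group number", where 1 is placebo and 2 is study drug. No block size or balance rule is given. The same section states "Each subject will be assigned a study identification (ID) number at screening, eg. subject #1, subject #2, subject #3 and so on", and then reads treatment from the table by that subject number. Section 6.2 repeats that the ID is issued at screening. No separate randomisation number is defined, and nothing says that the entry of a lost subject is reused or that the list may be extended.

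Several sections foresee ID holders who never reach treatment. Section 6.2 provides for the data of those who drop out of the process, "for subjects determined to not meet eligibility criteria or who later decline participation". Section 6.3 requires a log of screen failures. Section 5.6 states "If additional anti-inflammatory therapy (Restasis/ corticosteroids) is instituted during the wash-out period, the subject will be excluded from the study". OSDI is an inclusion criterion in Section 4.1 but is first scheduled on Day 1, so an ID holder can still prove ineligible then.

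Section 8.1 adds: "Subjects who withdraw due to an adverse event may be replaced".

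On numbers, Section 3.1 states: "Subjects will be randomly assigned to one of two groups (#1, #2), with at least 30 subjects per group". Section 7.1 aims for at least 30 per group to complete, from 72 enrolled with 20% dropout.

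On timing, the Schedule marks randomisation at Day 1 before dosing, and the title of Section 6.5.2 names Day 1 as the randomisation visit.

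**The concern.** A list as long as the enrolment target works only if every entry goes to an enrolled subject. Section 5.3 links entries to people who have merely been screened. The first ID holder lost before Day 1 takes an entry along, and 72 can no longer be randomised from the list. A replacement subject has no entry at all. The pharmacy would then have to improvise, although Section 5.3 intends a documented schedule and seed for reproducibility.

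Separately, independent draws do not guarantee any minimum arm size, although Section 3.1 promises one. At stake are the number randomised, the balance of the arms, and a clear record of how and when each subject was allocated.

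**Working it through.** **Inputs.** List length 72, no blocking (5.3). ID at screening (5.3, 6.2). At least 30 per group (3.1). 72 enrolled, 20% dropout, at least 30 completers per group (7.1). Assumptions: each entry is an independent draw with probability 0.5 for each group, and a share s of ID holders is lost before Day 1. The documents do not state s, so a range is shown.

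**Step 1: the plan's figure of 72.** 60 × 1.20 = 72 reproduces it. Allowing for 20% dropout requires 60 / (1 − 0.20) = 75, or 76 for equal arms (30 / 0.80 = 37.5, rounded up to 38 per arm). With 72, completers are 72 × 0.80 = 57.6, or 28.8 per group. Sixty completers from 72 requires dropout of at most 1 − 60/72 = 16.7%.

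**Step 2: balance with no losses.** Let X be the size of one arm, X ~ Binomial(72, 0.5).
- P(X = 36) = 9.4%.
- The 95% range for X is 28 to 44.
- P(30 ≤ X ≤ 42) = 87.5%, so the chance that one arm has fewer than 30 is 1 − 0.875 = 12.5%.

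**Step 3: losses before Day 1, reading Section 5.3 literally.** Expected number randomised = 72 × (1 − s). IDs needed to randomise 72 = 72 / (1 − s). For arm sizes, each entry is lost with probability s and falls in each arm with probability (1 − s)/2.

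| Assumed s | Expected randomised | IDs needed for 72 | Chance that an arm has fewer than 30 allocated |
|---|---|---|---|
| 0% | 72 | 72 | 12.5% |
| 10% | 64.8 | 80 | 49% |
| 20% | 57.6 | 90 | 93% |
| 30% | 50.4 | 103 | 99.9% |

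If exactly 65 were randomised, the last figure would be 46%; with fewer than 60 it is 100%. The rows for s above zero are scenarios. Only the direction is certain: one loss means fewer than 72.

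**Step 4: what blocking on Day 1 achieves.** It gives 72 randomised at 36:36, or close to it with varying blocks. At 20% dropout, 36 × 0.80 = 28.8 complete per group. If each subject drops out independently with probability 0.20, the chance that both groups reach 30 completers is 16% with 36:36 and 43% with 38:38. The repair to allocation therefore leaves the Step 1 shortfall in place.

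**The case against.** The strongest reply is that Day 1 is labelled the randomisation visit, the pharmacy runs the process, and the list length equals the number to be enrolled. The pharmacy may therefore intend to use the entries in order on Day 1, for enrolled subjects only. That reading is open, so a reader should not infer that the trial will certainly randomise fewer than 72. But Section 5.3 does not say it, and its text links the table to the screening ID. What stands is a conflict to reconcile. The Day 1 reading also leaves the list unblocked and without entries for replacements.

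Simple randomisation is valid, and moderate imbalance costs little. At 28:44, efficiency relative to 36:36 is 4 × 28 × 44 / 72² = 95%. Thirty is not a power threshold either, since Section 7.1 takes it from similar published trials without an effect size. This stands and limits the severity. It does not make good the minimum in Section 3.1.

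A reader might infer that extending the list would bias the trial. The documents do not support that: if entries are independent draws, further draws by the pharmacy are neutral, and research staff are masked. The cost is to the documented schedule.

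A reader might also count chance imbalance in washout status as a defect. It is inherent in randomisation, and unstratified blocks would not remove it. Section 7.2 plans to control for baseline imbalance, though it does not name washout.

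Finally, Section 4.3 says that those approached already have a low Schimer result and established symptoms, which may keep losses small. That is fair; the rates above are illustrations.

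**Conclusion.** The point holds and should be fixed, though it does not threaten the validity of the comparison. The sections disagree on when an allocation is used. On the literal reading of Section 5.3, any loss between screening and Day 1 leaves fewer than 72 randomised, about 65 at an assumed 10%, and replacements have no entry. On either reading, if the 72 entries are independent 1:1 draws, there is a 12.5% chance that an arm has fewer than 30 randomised before any dropout.

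It is tempting to conclude that allocation is why 30 per group will not be reached, and that blocking would cure it. The documents do not support this for completers. A perfect 36:36 split with no screening losses still leaves 28.8 per group at the stated 20% dropout. That is a separate arithmetic error in Section 7.1.

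**What to change.** Amend Section 5.3, and align Sections 6.2 and 6.5.2 with it, to say the following:

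- The screening ID serves identification only.
- On Day 1, once eligibility is confirmed and any washout is complete, the pharmacy assigns the next unused randomisation number.
- The numbers come from a concealed 1:1 permuted-block list with randomly varying block sizes, generated in advance with its seed recorded.
- The list holds spare entries beyond 72, and a replacement takes the next unused one.

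The cost is a short amendment and one regenerated list, with no extra visits or patients. Blocking makes allocation slightly more predictable; varying block sizes and masking limit this.

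Separately, correct Section 7.1: either state that 72 with 20% dropout is expected to give 57.6 completers (28.8 per group), or restate the enrolment figure as 75, or 76 for equal arms, which adds 3 or 4 subjects. Even 76 meets the target only on average (38 × 0.80 = 30.4 per group).
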